8.1.7. Seizure

8.2. Off-therapy criteria

8.2.1. Development of unacceptable toxicity during treatment:

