4.2. Dose Modifications

4.2.1. Check BUN/serum creatinine on post-op day 3.

4.2.2. If the patient has a seizure after the first dose and prior to the second dose, the second dose will not be given.

4.2.3. An anaphylactic reaction will be considered if the patient experiences any of the following 2 symptoms during infusion: nausea/vomiting; hives, pruritis or angioedema; dyspnea, wheezing or hypoxemia; syncope; or incontinence. A sudden decrease in systolic blood pressure by >30% based on age will also be considered evidence of anaphylaxis.

4.2.3.1. In case of anaphylactic reaction, immediately discontinue infusion of study agent.

4.2.3.2. Administer diphenhydramine 1 mg/kg IV (max dose 50 mg) and epinephrine 1 mg/ml (1:1000) 0.01 mg/kg IM, max dose 0.5 mg.

4.2.3.3. Additional supportive care including oxygen, bronchodilators, steroid and vasopressor support may be administered as appropriate.

4.2.3.4. The anesthesia provider will monitor continuously for signs of allergic reaction. These signs may include bronchospasm (increased airway pressures, difficulty with ventilation), and/or skin rash. Hypotension and tachycardia can be seen when an allergic reaction progresses to anaphylactic shock and may be suspected for hypotension unresponsive to fluid bolus. If an allergic reaction is suspected, a serum tryptase level will be drawn, while

treatment for allergic reaction (i.e., Epinephrine, anti-histamines) is commenced.

4.2.3.5. Medication Hypersensitivity and Anaphylaxis Treatment Guidelines can be found at:

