4.3.2. Allowed Concomitant Therapies

4.3.2.1. Patients may receive systemic therapies in accordance with their diagnosis, i.e., chemotherapy for patients with malignancy.

4.3.2.2. Patients with a history of reactions to transfusions may receive appropriate pre-medications (e.g. acetaminophen, diphenhydramine).

4.3.2.3. Medications that cause temporary impairment of platelet function should be used with caution.

4.3.2.4. All concomitant and supportive care medications should be documented.

4.3.3. NSAIDS will be given per standard postoperative pain protocol which is immediately after surgery.

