8.2.1.1. Acute kidney injury (defined by doubling of creatinine)

8.2.1.2. Anaphylaxis (grade 3 or 4).

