8.2.1.3. Seizure

8.2.2. Did not receive second dose of TXA/placebo due to unacceptable toxicity

8.2.3. Completed both doses of TXA/placebo

9. SAFETY AND ADVERSE EVENT REPORTING REQUIREMENTS

9.1. Reporting Adverse Experiences and Deaths to St. Jude IRB

9.1.1. Only “unanticipated problems involving risks to participants or others” referred to hereafter as “unanticipated problems” are required to be reported to the St. Jude IRB promptly, but in no event later than 10 working days after the investigator first learns of the unanticipated problem. Only adverse events that constitute unanticipated problems are reportable to the St. Jude IRB. The Common Terminology Criteria for Adverse Events (CTCAE) version 5 will be used to grade adverse events. As further described in the definition of unanticipated problem, this includes any event that in the PI’s opinion was:

- Unexpected (in terms of nature, severity, or frequency) given (1) the research procedures that are described in the protocol-related documents, such as the IRB-approved research protocol and informed consent document, as well as other relevant information available about the research; (2) the observed rate of occurrence (compared to a credible baseline for comparison); and (3) the characteristics of the subject population being studied; and
- Related or possibly related to participation in the research; and

- Serious; or if not serious suggests that the research places subjects or others at a greater risk of harm (including physical, psychological, economic, or social harm) than was previously known or recognized.

Unrelated, expected deaths do not require reporting to the IRB. Though death is “serious”, the event must meet the other two requirements of “related or possibly related” and “unexpected/unanticipated” to be considered reportable.

Deaths meeting reporting requirements are to be reported immediately to the St. Jude IRB, but in no event later than 48 hours after the investigator first learns of the death.

9.1.2. The following definitions apply with respect to reporting adverse experiences:

9.1.2.1. Serious Adverse Event: Any adverse event temporally associated with the subject’s participation in research that meets any of the following criteria:

- results in death;
- is life-threatening (places the subject at immediate risk of death from the event as it occurred);
- requires inpatient hospitalization or prolongation of existing hospitalization;

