The patients who receive only one dose due to anaphylaxis (grade 3 or 4) or seizure will be removed from the evaluation of all objectives. The anticipated rate of each toxicity is about 1%. However, the descriptive statistics will be calculated for these patients who receive only one dose, e.g., adverse events and endpoints in all the objectives. The expected accrual number for our study will be 39 patients (to yield 38 evaluable subjects).

Unacceptable toxicities consist of acute kidney injury (defined by doubling of creatinine) or anaphylaxis (grade 3 or 4) or thrombotic event or seizure. The anticipated rate of each toxicity is about 1%. Thrombotic events occurring six weeks beyond the time of surgery will not be considered related to TXA administration. A heuristic approach is used to monitor each of the three toxicities in the TXA group. For each toxicity, starting from the 3rd patient, if the number of patients with any toxicity is equal to or larger than 3, the study accrual will be paused and amendments to the protocol will be discussed with the IRB. This monitoring rule yields the largest type-I error rate 0.044 when the 20th (one patient is removed due to not receiving the 2nd dose) patient show the toxicity (the 20th patient and any two previous patients in the TXA group).

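### Seizure is an off-study as well as an off-therapy criterion, which ends follow-up that section 11.1 relies on

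*Combined protocol and SAP*

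**What the plan says.** The off-study list in section 8.1 contains death, loss to follow-up, patient or parent request, completion, PI discretion and ineligibility, and then "8.1.7. Seizure". The entry carries no qualifier. The off-therapy list in section 8.2 has the same event, "8.2.1.3. Seizure", next to creatinine doubling and "8.2.1.2. Anaphylaxis (grade 3 or 4"). Neither of those two appears in section 8.1.

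For dosing, section 4.2.2 states: "If the patient has a seizure after the first dose and prior to the second dose, the second dose will not be given". A patient who seizes between doses is therefore a one-dose patient for section 11.1. That section says patients with a single dose because of grade 3 or 4 anaphylaxis "or seizure will be removed from the evaluation of all objectives", but adds that "the descriptive statistics will be calculated for these patients who receive only one dose, e.g., adverse events and endpoints in all the objectives".

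Planned follow-up runs to 6 months (sections 6.2 and 10.1, Appendix I). Section 6.4 lists a wound evaluation and a physical therapy functional assessment as off-study evaluations, without timing. Section 6.5 provides for no long-term follow-up.

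**The concern.** Stopping a drug and stopping observation are separate decisions. Section 8.2.1.3 handles the first. Section 8.1.7 adds the second for one toxicity only, and the protocol gives no reason for treating seizure differently from the others.

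Section 5.1 lists seizure as a rare TXA reaction, so loss of follow-up through 8.1.7 can depend on treatment. At stake is the later course of patients who had one of the toxicities that section 11.1 monitors: other adverse events, including thrombosis within the six weeks that 11.1 treats as possibly TXA-related, and their transfusion, drain, wound and functional outcomes. Section 11.1 also commits to a description that the collected data could not fully support.

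**Working it through.** **1. How each unacceptable toxicity in section 11.1 is handled in section 8.**

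| Toxicity | Off therapy (8.2) | Off study (8.1) |
|---|---|---|
| Creatinine doubling | 8.2.1.1 | no |
| Anaphylaxis, grade 3 or 4 | 8.2.1.2 | no |
| Seizure | 8.2.1.3 | 8.1.7 |
| Thrombotic event | not listed | not listed |

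**2. Does off-study end follow-up?** The protocol does not define the term, so this is an inference from three places.
- Section 8.2.3 takes every patient who completes both doses off therapy, about 6 hours after the first dose, yet follow-up runs to 6 months. Off-therapy therefore already means that dosing is over and observation continues. Off-study must mean something more.
- Section 8.1.4 ties the ordinary exit from the study to having finished follow-up as well as treatment.
- No section says that collection continues after a patient is off study.

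**3. What would be kept and what would be lost.**
- *Seizure between doses.* Kept: data up to the seizure, the seizure as an adverse event, and the 6.4 wound and functional evaluations. Lost under the protocol: post-operative transfusion and drain output, adverse events over the following six weeks, FMA and PROMIS at 6 weeks, 3 months and 6 months, and scheduled wound visits. Section 11.1 promises to describe these endpoints for this patient.
- *Seizure after both doses, at any time to 6 months.* The 11.1 removal covers only one-dose patients, so this patient stays evaluable, but scheduled assessments after the seizure are missing. The cause need not be study drug. Section 4.3.2.1 allows other treatment in this period: "Patients may receive systemic therapies in accordance with their diagnosis, i.e., chemotherapy for patients with malignancy".

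**4. The plan's own accrual figure.** Inputs from section 11.1: 38 evaluable patients, and removal for anaphylaxis (about 1%) or seizure (about 1%), 2% together. Then 38 / (1 − 0.02) = 38.8, rounded up to 39, which matches the plan. The 19 per group is also reproduced: a Welch t-test with means 2.906 and 2.435, SDs 0.507 and 0.488, and two-sided alpha 0.05 has power 0.810 at 19 per group and 0.788 at 18.

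**5. How many patients.** For seizure rate p and n patients, the expected number is np and the chance of at least one is 1 − (1 − p)^n.
- p = 0.01, n = 39: 39 × 0.01 = 0.39; 1 − 0.99^39 = 0.32.
- p = 0.01, n = 20 (about one arm): 20 × 0.01 = 0.20; 1 − 0.99^20 = 0.18.

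The 1% is the plan's rate for the toxicity. Section 8.1.7 covers seizure from any cause over 6 months, and the documents give no rate for that. Over an assumed range of 0.5% to 5%, the chance of at least one among 39 runs from 0.18 to 0.86 (0.55 at 2%). Nothing in the documents supports the upper end, and sections 3.2.10 and 3.2.16 exclude a history of seizures (other than febrile) and of CNS disease.

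**The case against.** The strongest reply is that little is really lost. A reader might infer from 8.1.7 that these patients would have no data at all. The documents do not support that: pre-seizure data and the section 6.4 evaluations exist, and estimated blood loss and intra-operative transfusion exist when the seizure follows surgery. Appendix III also classes every assessment except ROTEM and TXA as standard of care, so much would still be charted. This stands in part. However, section 6.4 lists no transfusion, drain or adverse-event follow-up, an evaluation near surgery cannot replace the 6-, 12- and 24-week outcomes, and no text provides for using charted data after off-study.

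A reader might also infer that the monitored seizure goes uncounted. It does not: the section 11.1 pause rule counts patients with a toxicity, and the seizure itself is captured. Only later events in that patient could be missed.

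Nor is the primary comparison materially damaged. Section 11.1 already removes one-dose seizure patients from all objectives, and the one spare patient in the accrual of 39 already allows for this. An evaluable patient's transfusion total is cut short only if the seizure comes after the second dose and within the transfusion period, which is days 1 to 6 in Appendix VI or until chemotherapy resumes in 1.2.4. A seizure at month 4 costs no primary data under Appendix VI. These points stand, and they limit the size of the concern.

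**Conclusion.** The point holds as an internal conflict with a small expected count. Sections 8.1.7 and 11.1 cannot both be carried out as written for a patient who seizes between doses, and 8.1.7 creates avoidable missing data in a patient who seizes later. At the plan's 1% rate the most likely outcome is no affected patient (probability 0.68), and the chance of at least one is 0.32.

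The affected data are mainly secondary, exploratory and late safety data. They still matter because the loss can be related to treatment and falls on patients with a monitored toxicity. The conclusion rests on reading off-study as the end of scheduled follow-up, which section 8 supports but does not state. If the sponsor means otherwise, the text should say so.

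**What to change.** Delete 8.1.7. Leave the off-therapy and dosing rules (8.2.1.3 and 4.2.2) as they are.

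Then reconcile sections 8.1, 8.2, 6.4 and 11.1 with one sentence: patients off therapy for any unacceptable toxicity stay on study for transfusion, adverse event, wound and functional follow-up through 6 months, unless another off-study criterion (8.1.1 to 8.1.6) applies. Keeping all six preserves withdrawal on request, PI discretion and removal for ineligibility. The deletion alone settles the case of a seizure after both doses.

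The cost is one deleted line, one added sentence and a few more follow-up records. The visits are already scheduled and, by Appendix III, standard of care. Accrual stays at 39 and the group size at 19, because the section 11.1 removal of one-dose patients is unchanged.

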8.2.1.1. Acute kidney injury (defined by doubling of creatinine)

8.2.1.2. Anaphylaxis (grade 3 or 4).

8.2.1.3. Seizure

8.2.2. Did not receive second dose of TXA/placebo due to unacceptable toxicity

8.2.3. Completed both doses of TXA/placebo

9. SAFETY AND ADVERSE EVENT REPORTING REQUIREMENTS

9.1. Reporting Adverse Experiences and Deaths to St. Jude IRB

9.1.1. Only “unanticipated problems involving risks to participants or others” referred to hereafter as “unanticipated problems” are required to be reported to the St. Jude IRB promptly, but in no event later than 10 working days after the investigator first learns of the unanticipated problem. Only adverse events that constitute unanticipated problems are reportable to the St. Jude IRB. The Common Terminology Criteria for Adverse Events (CTCAE) version 5 will be used to grade adverse events. As further described in the definition of unanticipated problem, this includes any event that in the PI’s opinion was:

- Unexpected (in terms of nature, severity, or frequency) given (1) the research procedures that are described in the protocol-related documents, such as the IRB-approved research protocol and informed consent document, as well as other relevant information available about the research; (2) the observed rate of occurrence (compared to a credible baseline for comparison); and (3) the characteristics of the subject population being studied; and
- Related or possibly related to participation in the research; and

- Serious; or if not serious suggests that the research places subjects or others at a greater risk of harm (including physical, psychological, economic, or social harm) than was previously known or recognized.

Unrelated, expected deaths do not require reporting to the IRB. Though death is “serious”, the event must meet the other two requirements of “related or possibly related” and “unexpected/unanticipated” to be considered reportable.

Deaths meeting reporting requirements are to be reported immediately to the St. Jude IRB, but in no event later than 48 hours after the investigator first learns of the death.

9.1.2. The following definitions apply with respect to reporting adverse experiences:

9.1.2.1. Serious Adverse Event: Any adverse event temporally associated with the subject’s participation in research that meets any of the following criteria:

- results in death;
- is life-threatening (places the subject at immediate risk of death from the event as it occurred);
- requires inpatient hospitalization or prolongation of existing hospitalization;
- results in a persistent or significant disability/incapacity;
- results in a congenital anomaly/birth defect; or
- any other adverse event that, based upon appropriate medical judgment, may jeopardize the subject’s health and may require medical or surgical intervention to prevent one of the other outcomes listed in this definition (examples of such events include: any substantial disruption of the ability to conduct normal life functions, allergic bronchospasm requiring intensive treatment in the emergency room or at home, blood dyscrasias or convulsions that do not result in inpatient hospitalization, or the development of drug dependency or drug abuse), a congenital anomaly/birth defect, secondary or concurrent cancer, medication overdose, or is any medical event which requires treatment to prevent any of the medical outcomes previously listed.

9.1.2.2. Unexpected Adverse Event:

- Any adverse event for which the specificity or severity is not consistent with the protocol-related documents, including the applicable investigator brochure, IRB approved consent form, Investigational New Drug (IND) or Investigational Device Exemption (IDE) application, or other relevant sources of information, such as product labeling and package inserts; or if it does appear in such documents, an event in which the specificity,

severity or duration is not consistent with the risk information included therein; or

- The observed rate of occurrence is a clinically significant increase in the expected rate (based on a credible baseline rate for comparison); or
- The occurrence is not consistent with the expected natural progression of any underlying disease, disorder, or condition of the subject(s) experiencing the adverse event and the subject's predisposing risk factor profile for the adverse event.

9.1.2.3. Internal Events: Events experienced by a research participant enrolled at a site under the jurisdiction of St. Jude IRB single-center research projects.

9.1.2.4. Unanticipated Problem Involving Risks to Subjects or Others: An unanticipated problem involving risks to subjects or others is an event which was not expected to occur and which increases the degree of risk posed to research participants. Such events, in general, meet all of the following criteria:

- unexpected;
- related or possibly related to participation in the research; and
- suggests that the research places subjects or others at a greater risk of harm (including physical, psychological, economic, or social harm) than was previously known or recognized. An unanticipated problem involving risk to subjects or others may exist even when actual harm does not occur to any participant.

Although some adverse events will qualify as unanticipated problems involving risks to subjects or others, some will not; and there may be other unanticipated problems that go beyond the definitions of serious and/or unexpected adverse events. Examples of unanticipated problems involving risks to subjects or others include:

- Improperly staging a participant's tumor resulting in the participant being assigned to an incorrect arm of the research study;
- The theft of a research computer containing confidential subject information (breach of confidentiality); and
- The contamination of a study drug. Unanticipated problems generally will warrant consideration of substantive changes in the research protocol or informed consent process/document or other corrective actions in order to protect the safety, welfare, or rights of subjects or others.

9.1.2.5 There will be an assessment for the existence of adverse events with each study participant encounter, i.e. during each history and/or physical, as depicted in Appendix I. The study team will capture all Grade 3-5 adverse events, including lab toxicities. All adverse events will be assessed for seriousness, grade,

attribution/ causality, and duration. Adverse events will be recorded in the database and reported as per institutional policy. The study team and the PI will review adverse events/toxicities during regular study team meetings. Once adverse events/toxicities have been reviewed, the PI will sign and date a study AE document.

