1.3 Exploratory Objectives

1.3.1. To evaluate differences in functional outcomes post-operatively for patients randomized to receive perioperative TXA versus placebo.

- Study endpoint: Functional Mobility Assessment (FMA), quality of life endpoints and Patient-Reported Outcomes Measurement Information System (PROMIS), quality of life endpoints.

1.3.2. To explore if significant correlations are observed between parameters reported with rotational thromboelastometry (ROTEM®) and EBL and transfusion requirements

in pediatric and young adult patients undergoing limb salvage procedure who are randomized to perioperative TXA versus placebo.

- Study endpoint: rotational thromboelastometry (ROTEM), continuous measurement; intra- or post-operatively transfused blood volume (mL/kg), continuous measurement; estimated blood loss (EBL), continuous measurement.

1.3.3. To evaluate differences in the prevalence and management of wound complications such as superficial or periprosthetic infections, wound dehiscence, contact dermatitis, post-operative hematomas, or any other clinically significant wound complication between patients randomized to receive perioperative TXA versus placebo.

- Study endpoint: Number of patients with the wound complications of interest.

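### Required adverse event capture starts at Grade 3, but the pausing rule counts creatinine doubling, thrombotic events and seizures at any grade, so some qualifying events have no required route into the count

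*Combined protocol and SAP*

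**What the plan says.** **Capture.** Section 9.1.2.5 has adverse events looked for at each participant encounter and then sets the scope: "The study team will capture all Grade 3-5 adverse events, including lab toxicities". The next sentence begins "All adverse events will be assessed for seriousness, grade" and goes on to attribution and duration. No section expressly requires Grade 1-2 events to be recorded, and none sets up a separate collection for the pausing rule.

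**Pausing rule.** Section 11.1 defines what is counted: "Unacceptable toxicities consist of acute kidney injury (defined by doubling of creatinine) or anaphylaxis (grade 3 or 4) or thrombotic event or seizure". Anaphylaxis carries a grade. Creatinine doubling and seizure do not, and thrombotic events carry only a six-week limit. Each toxicity is anticipated at about 1%. The action is stated as "if the number of patients with any toxicity is equal to or larger than 3, the study accrual will be paused", and the operating characteristic as "This monitoring rule yields the largest type-I error rate 0.044 when the 20th" TXA patient shows the toxicity.

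**Other routes by which an event could be noticed.**
- Seizure withholds the second dose (4.2.2). It is also an off-study criterion (8.1.7) and an off-therapy criterion (8.2.1.3), and convulsions are a named example in the serious adverse event definition (9.1.2.1).
- Creatinine doubling is an off-therapy criterion for toxicity during treatment (8.2.1.1) and a condition on the second dose (Appendix IV). The metabolic panel is scheduled in surgery, daily while inpatient, on post-operative day 3 and at one week (6.2 table).
- Thrombotic event is not in the 8.2.1 list and has no scheduled test.

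**The concern.** The rule selects events by definition, while the data collection selects them by grade. Where the two differ, staff can follow section 9.1.2.5 exactly and still leave out an event that section 11.1 says should count.

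The threshold is three patients among about 20 on TXA, so one or two unrecorded events can decide whether accrual pauses. The error runs one way: under-capture can only make a pause less likely. Section 4.4.1 itself says these children may be at higher risk of clots than people in earlier TXA studies, because of their cancer and possible central lines. Thrombosis is also the toxicity with the weakest alternative route into the count.

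**Working it through.** **Step 1. Reproduce the plan's figure.** Inputs from 11.1: n = 20 TXA patients, threshold 3, four listed toxicities at about 1% each. Let X be the number of patients with a counted toxicity, binomial(20, p).

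P(X ≥ 3) = 1 − P(0) − P(1) − P(2)

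With p = 4 × 0.01 = 0.04: 1 − 0.4420 − 0.3683 − 0.1458 = 0.0439, which is the stated 0.044.

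One toxicity alone (p = 0.01) gives 0.0010, and three pooled (p = 0.03) give 0.0210. Of the versions tried, only 20 patients at a pooled 4% return 0.044. So the stated figure assumes that all four toxicities are pooled and that every qualifying event is counted. (Section 11.1 also says "A heuristic approach is used to monitor each of the three toxicities in the TXA group" although it lists four. That is a separate wording point.)

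**Step 2. Trace each toxicity to the count.**

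| Toxicity in 11.1 | Grade limit in 11.1 | Required record if graded below 3 |
|---|---|---|
| Anaphylaxis | 3 or 4 | Not applicable; always within Grade 3-5 |
| Seizure | None | Off-study and off-therapy criteria; serious event example |
| Creatinine doubling | None | Off-therapy criterion, during treatment only |
| Thrombotic event | None (six-week limit) | Only if it meets the serious event definition |

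Treatment is two doses 6 hours apart (4.1.3), and completing both takes the patient off therapy (8.2.3). A doubling first seen on a later inpatient day, on day 3 or at one week would be in the laboratory data. Unless it is Grade 3 or higher, or serious, nothing requires it to be logged as an event.

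**Step 3. Size under assumed capture shares.** The documents do not give the share c of qualifying events that would be Grade 3 or higher or otherwise recorded. It is an assumption. Let r be the rate per toxicity, with anaphylaxis fully captured and c applied to the other three:

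p = r + 3rc

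| r per toxicity | Pooled rate | c | p counted | P(X ≥ 3) of 20 |
|---|---|---|---|---|
| 1% (plan) | 4% | 100% | 0.0400 | 0.044 |
| 1% | 4% | 75% | 0.0325 | 0.026 |
| 1% | 4% | 50% | 0.0250 | 0.013 |
| 2.5% (assumed) | 10% | 100% | 0.1000 | 0.32 |
| 2.5% | 10% | 70% | 0.0775 | 0.20 |
| 2.5% | 10% | 50% | 0.0625 | 0.13 |

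The 1% rows show how far the rule departs from its stated operating characteristic. The 10% rows show the loss of sensitivity when toxicity exceeds expectation.

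**Step 4. Treat seizure as fully captured too.** Then p = 2r + 2rc. At r = 1% and c = 50%, p = 0.03 and the chance is 0.021. At r = 2.5%, p = 0.085 gives 0.24 (c = 70%) and p = 0.075 gives 0.19 (c = 50%). The loss is smaller but in the same direction.

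**The case against.** The strongest reply is that the Grade 3-5 sentence sets a minimum and forbids nothing. The sentences after it speak of adverse events without a floor, and section 9.3.1 sends non-serious events to the FDA in the annual report. On this view, a team applying the 11.1 rule must identify the named events anyway. It is true that lower-grade recording is not prohibited. But the Grade 3-5 sentence is the only stated scope, and the next sentence reads most naturally as describing the events so captured; otherwise the grade limit would do no work.

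Second, the gap exists only if such events can be graded below 3, which depends on CTCAE version 5.0, cited but not reproduced. This stands. It is why no grade is asserted here and the size is shown as a range.

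Third, other routes exist. This largely disposes of seizure. It narrows creatinine doubling, since the values will be available. For thrombosis, the serious event definition has no grade floor and takes in events needing treatment to prevent a listed outcome; serious events are recorded (9.3.2) and monitored (10.2). That leaves only thromboses that are both below Grade 3 and not serious.

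Three stronger readings are tempting but not supported:
- A reader might infer that minor wound complications under objective 1.3.3 are also lost. They have their own collection: nursing review of the incision (6.2.9), recording of dehiscence and hematoma (6.2.10), CTCAE grading without a floor (6.3.3) and scheduled follow-up to 6 months (Appendices I and VI).
- A reader might infer that a TXA-versus-placebo adverse event comparison is compromised. Apart from the wound-complication comparison, section 11 specifies no between-arm adverse event comparison.
- A reader might apply the capture share to the whole pooled rate. At 10% and half captured, p = 0.05 and the chance is 0.08. That thins anaphylaxis as well, which is Grade 3 or 4 by definition and always captured.

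**Conclusion.** The concern holds in a limited form. The capture rule and the pausing rule use different criteria, and no section bridges them. The exposure is clearest for thrombotic events and for creatinine doubling after the second dose, and it is small for seizure. The plan's own 0.044 presumes complete counting.

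If half of the three ungraded toxicities were captured, that figure would be 0.013. At an assumed 10% pooled rate, split equally, the chance of pausing would drop from 0.32 to 0.20 or 0.13 at 70% or 50% capture. These results assume independent patients, pooled counting as implied by 0.044, at most one toxicity per patient (rates simply added) and capture shares that the documents do not supply. The direction is certain; the size is not. The documents do not show that events will in fact be missed, only that the plan as written permits it.

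**What to change.** In 9.1.2.5 and the e-CRF, require a record of every event that meets the 11.1 toxicity definitions, regardless of CTCAE grade: creatinine doubling, thrombotic event, seizure, and anaphylaxis as defined there. State in 11.1 that the pausing count is taken from those records. Keep the Grade 3-5 scope for all other adverse events.

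The cost is a few e-CRF fields and slightly more data entry in 39 patients. Treatment, sample size and the rule itself are unchanged. With every qualifying event counted, p stays at 0.04 and the type I error stays at the stated 0.044.
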